1. STUDY OBJECTIVES

This is a phase II, prospective, longitudinal, multi-center trial of poly-ICLC (Hiltonol ®) treatment for progressive low-grade gliomas in pediatric patients with NF1. The primary objective is to evaluate the efficacy of poly-ICLC in pediatric NF1 patients with progressive low-grade glioma (LGG) as measured by objective tumor response rate (CR+PR) within the first 48 weeks (12 cycles) of therapy.

The secondary objectives are to:

- a) Determine 12, 24 and 60 month progression free survival (PFS) in pediatric NF1 patients with progressive LGG treated with poly-ICLC.
- b) Evaluate the efficacy of poly-ICLC in pediatric NF1 patients with progressive LGG as measured by best objective tumor response rate (CR+PR) within 24 cycles of therapy.
- c) Evaluate the efficacy of poly-ICLC in pediatric NF1 patients with progressive LGG as measured by clinical benefit response rate (CR+PR+MR+SD) after 12 and 24 cycles of therapy.
- d) Assess the toxicity associated with poly-ICLC treatment in pediatric NF1 patients with LGG.

Exploratory objectives are to:

- a) Evaluate the visual outcome measures in children with progressive optic pathway gliomas treated with poly-ICLC. Visual response is defined as 0.2 logMAR or greater in acuity improvement.
- b) Evaluate patient reported outcomes and quality of life measures.
- c) Evaluate biological correlates.
- d) Compare RANO and RAPNO response determinations in this population.

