14. STATISTICAL CONSIDERATIONS

Primary Endpoints

The primary endpoint of the study is objective response rate (defined as CR or PR) during the first 12 months of treatment. Response will be assessed through the time of the post-12th cycle tumor assessment, or through the last tumor assessment time during this nominal period for patients in follow-up but who have withdrawn from protocol therapy, or through the last available tumor assessment for patients who are lost to follow-up during this time.

The percent change in tumor sizes compared to baseline will be recorded at each evaluation time and will be used to define the categorical response as described below, per the definition of CR, PR, MR, SD, and PD in section 10.4.

- For tumors that regress compared to baseline during the assessment period without first satisfying the criteria for progressive disease (PD), response will be defined at the nadir of the tumor size compared to baseline provided that the percent reduction at the nadir satisfies the definition of CR, PR, or MR per section 10, with the response value of CR, PR, or MR determined by the percent reduction at this time.

The associated time of response will also be recorded.

- For tumors that progress compared to baseline and satisfy the definition of PD without first satisfying the criterion at least for minor response (MR), response will be defined at the first time at which the percent increase in tumor size compared to baseline satisfies the criterion for PD. The response value will be PD. The associated time of response will also be recorded. Progressive disease could be confirmed with a short follow-up MRI (+/- 6 weeks) per treating physician decision, otherwise continue with MRI interval per protocol.
- For tumors that neither regress sufficiently to satisfy the criterion for MR nor progress sufficiently to satisfy the criterion for PD during the assessment period, the response value will be determined to be SD.

Patients will be considered evaluable for response if they have received at least one dose of treatment and have at least one post-baseline tumor assessment.

Patients who undergo gross total resection while on study will be excluded from further response at the time of surgery. Patients who have measurable residual disease (at least twice the thickness of the MRI slide) after resection will be able to continue study drug and the post-op MRI will be used as the new baseline.

Secondary Endpoints

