- Progression free survival (PFS), defined as the time from start of treatment to the first occurrence of tumor recurrence, tumor progression, occurrence of a second malignancy, or death from any cause. Patients event-free at last follow-up will be censored in analysis. PFS will be determined at 12, 24 and 60 months.
- Objective response rate (defined as CR or PR) after 24 cycles of treatment. Response will be assessed through the time of the post-24th cycle tumor assessment, or through the last tumor assessment time during this nominal period for patients in follow-up, but who have withdrawn from protocol therapy, or through the last available tumor assessment for patients who are lost to follow-up during this time.
- Clinical benefit defined as (CR+PR+MR+SD). Clinical benefit will be assessed through the time of the post-12 and 24th cycle tumor assessment, or through the last tumor assessment time during this nominal period for patients in follow-up but who have withdrawn from protocol therapy, or through the last available tumor assessment for patients who are lost to follow-up during this time.
- The grade and duration of CTCAE toxicities observed during treatment using CTAE version 5.0.
- Evaluation for visual acuity for patients with optic pathways gliomas will be assessed at 12 months and 24 months from starting therapy. Patient visual outcome will be assessed through the time of the post-12th and 24th cycle visual assessment, or through the last visual assessment time during this nominal period for patients in follow-up but who have withdrawn from protocol therapy, or through the last available tumor assessment for patients who are lost to follow-up during this time.

Exploratory Endpoint

The RANO criteria for response assessment will be determined and descriptively compared to the primary response using RAPNO.

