Based on the safety analysis set, information regarding study treatment administration, drug dosing and cycle compliance, safety variables, will be described and summarized. Data from the biological analysis will also be described and summarized. Safety will be assessed via tabulations of AEs and SAEs as well as Diary recordings following treatment dose/cycle of therapy.

All analyses for outcome results will be based on evaluable participants, as defined in section 14.

At the end of the trial, we will report poor performance if the treatment is rejected when not meeting the criteria of at least 3 responders' cases. If there is no success, we will report a failure to reject the null hypothesis. If the null hypothesis is rejected, the probability of the estimated success rate will be reported and 95% confidence intervals as well as the distribution of changes in tumor size.

Dose-limiting toxicity (DLT) is not an objective in this trial. Toxicity will be continuously monitored.

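### Clinical benefit after 12 and 24 cycles is scored as best status in the period, so one stable week-12 scan followed by loss to follow-up counts as benefit at week 96

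*Combined protocol and SAP*

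**What the plan says.** Section 1 sets a secondary objective on the "clinical benefit response rate (CR+PR+MR+SD) after 12 and 24 cycles of therapy", and the Protocol Summary lists the endpoint in similar terms. Section 14, Secondary Endpoints, makes it operational: "Clinical benefit will be assessed through the time of the post-12 and 24th cycle tumor assessment". For patients off protocol therapy but still followed, the last scan within the period is used. The third route is "through the last available tumor assessment for patients who are lost to follow-up during this time".

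The categories come from the rules earlier in Section 14:
- A tumor that shrinks without first meeting PD is classified at its smallest size, as CR, PR or MR.
- A tumor that meets PD before reaching MR is classified PD.
- For tumors that neither reach MR "nor progress sufficiently to satisfy the criterion for PD during the assessment period, the response value will be determined to be SD".

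No minimum duration of SD is given there or in section 10.5. Patients are evaluable if they "have received at least one dose of treatment and have at least one post-baseline tumor assessment". Section 14.3 adds: "All analyses for outcome results will be based on evaluable participants, as defined in section 14".

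**The concern.** A response rate needs observed shrinkage, so assessing it through the last scan credits only what was seen. SD needs only that progression was not seen. Once SD counts as success, the same rule turns an absence of later scans into success at a later time point.

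The label points to status at 48 and 96 weeks, while the rule gives best status at any point up to then. A reader of the final report would take a 24-cycle clinical benefit rate as the share of patients still without progression at about two years. The rule does not support that reading for patients lost early, or for patients who responded and then progressed. The plan also treats one patient in two ways: a patient lost while event-free is censored for PFS but is a success for clinical benefit.

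**Working it through.** **Inputs.** Cycles last 28 days; the first scan is at the end of cycle 3 (+/- 2 weeks) and scans then follow every 3 cycles (Protocol Summary). There are 16 evaluable patients (section 14.2). The number lost after a stable scan is not in the documents and is assumed below. The Section 14 category rules stand under the primary endpoint; I apply them to clinical benefit because no other rule is given.

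**The plan's own figures.** None is stated for clinical benefit. The 16 comes from the primary design, which reproduces. With X binomial(16, p) and success at X >= 3, P(X >= 3 | 0.05) = 0.0429 (stated 0.043) and P(X <= 2 | 0.25) = 0.1971 (stated 0.197).

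**Timing.** 3 x 28/7 = 12 weeks; 12 x 28/7 = 48 weeks; 24 x 28/7 = 96 weeks.

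**Four patients under the rules** (scan weeks for the second are illustrative):

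| Course | Scored at cycle 24 | Comment |
|---|---|---|
| Stable at week 12, then lost | SD, benefit | 96 - 12 = 84 weeks unobserved; also benefit at week 48 |
| MR at week 24, PD at week 60 | MR, benefit | Classified at the smallest size; the later PD does not change it |
| Stable at week 12, stops drug, PD on a later scan in the period | PD, no benefit | Scans continue off therapy (sections 3.5 and 5.4, Appendix 4) |
| Stable at week 12, then new tumor therapy or consent withdrawn | Not stated | Off study by section 3.5; Section 14 names only loss to follow-up |

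**Size.** Let b be patients with benefit documented at cycle 24 and L those lost after one stable scan. The plan reports (b + L)/16. Counting the lost as not benefiting gives b/16; leaving them out gives b/(16 - L). The first two differ by L/16, or 6.25 points per patient. Taking b = 8 as an assumption:

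| L | Plan | Lost counted as not benefiting | Lost left out |
|---|---|---|---|
| 0 | 50.0% | 50.0% | 50.0% |
| 1 | 56.3% | 50.0% | 53.3% |
| 2 | 62.5% | 50.0% | 57.1% |
| 4 | 75.0% | 50.0% | 66.7% |

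For L = 4 the exact (Clopper-Pearson) 95% intervals are 47.6 to 92.7% under the plan and 24.7 to 75.3% with the lost counted as not benefiting. With b = 4 and L = 4 the three rates are 50.0%, 25.0% and 33.3%.

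**Against true status.** If a share s of the lost patients in fact stayed progression-free, the overstatement is L(1 - s)/16. For L = 4 it is 25 points at s = 0, 12.5 at s = 0.5 and 0 at s = 1. So L/16 is a maximum.

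**Scan windows.** Suppose a patient stops drug at week 24. Off-therapy scans at 12 and 18 months fall near weeks 24 + 52 = 76 and 24 + 78 = 102, the latter with a window of 98 to 106 weeks. The on-therapy cycle-24 window is 94 to 98. A fully compliant patient need not have a scan in it.

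**The case against.** The strongest reply is that this is a best-response-in-period endpoint with a loose label. Section 14 also uses the word after for 24-cycle objective response, which Section 1 calls best response within 24 cycles. On that view relabelling is enough. This has force: the rule is smallest size or first PD, not a plain carry-forward of the last scan. But Section 1 itself words the two objectives differently, within for best response and after for clinical benefit. Relabelling alone would also leave SD with no minimum duration.

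Second, SD requires clinical stability (section 10.4), visual progression is defined (section 9.5), and symptomatic deterioration is reported separately. This narrows the group but does not reach a patient who was stable at week 12 and unseen afterwards.

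Third, counting every lost patient as a failure is biased downward. Section 2.1 reports a 2-year PFS of 96% with selumetinib and a 5-year EFS of 69% in NF1 patients on carboplatin and vincristine. Those are other drugs, but they make it extreme to assume that every lost patient progressed. This stands, and it is why the stricter figure should be presented as a lower bound.

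Fourth, the endpoint is descriptive with no decision rule, PFS at 12, 24 and 60 months covers progression with censoring, and the Consort diagram will show withdrawals. This limits the consequence without making the reported rate mean what its label says.

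**Conclusion.** The point holds as a mismatch between label and rule for a secondary, descriptive endpoint. Two groups count as benefit at 24 cycles without evidence of it: patients lost after an early stable scan, and patients with MR or better who later progress. The first group adds at most 6.25 points each at n = 16. One to four such patients, giving 6.25 to 25 points, is an illustration and not a forecast. The result assumes that the Section 14 categories apply to clinical benefit as written.

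A reader might infer more, and the documents do not support it:
- That everyone who withdraws is carried forward. Stopping the drug does not end MRI follow-up, so later PD within the period can still be captured.
- That patients who start new tumor therapy are carried forward as benefit. Section 3.5 takes them off study, but Section 14 does not say how they, or patients who withdraw consent, are scored. That is a gap, not a stated rule.
- That the 25% unevaluable allowance supports four lost patients among the 16. Unevaluable patients lack a dose or any post-baseline scan and sit outside the 16, between 16 evaluable and 20 enrolled.
- That the primary CR+PR test is affected. It is not, since SD is never a success there.

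**What to change.** In Section 14, Secondary Endpoints, define clinical benefit at cycle 12 (and 24) as follows:
- **Benefit:** the first scheduled scan at or after the time point, taken within the window of the schedule the patient is on, shows no PD, with no PD and no new tumor-directed therapy before it. On therapy, this is the cycle-12 or cycle-24 scan with its 2-week window; off therapy, it is the next scan under section 5.4 with that schedule's window. PD is as defined in section 10.4, including its provision for suspected pseudoprogression.
- **Benefit not documented:** evaluable patients without such a scan. They stay in the denominator, and the rate is described as a conservative lower bound. State that this covers loss to follow-up, withdrawn consent and going off study for new therapy.
- **Gross total resection:** keep the existing Section 14 exclusion.
- **Sensitivity analysis:** report the current rule, labelled best response of SD or better within 12/24 cycles.

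The cost is SAP wording; no scans are added. The reported rate will be less favorable and may understate benefit for lost patients who in fact stayed stable. Showing both figures makes that range visible.

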9.1. Visual Acuity (best corrected)

IMPORTANT NOTE: if the VA data at a particular visit is felt to be unreliable due to poor cooperation, testing should be repeated within 4 weeks. Only the visit believed to have yielded the most reliable data should be reported.

Teller acuity testing using TAC II cards will be attempted on all participants at all visits. All VA testing will be performed by study personnel who have undergone TAC teaching by the study team. VA testing will be performed in each eye separately at a distance of 55 cm in all participants. The tester will utilize the “Two down, one up” protocol to achieve the best visual acuity. Acuity will be reported in cycles/cm by the site and converted by the operations center to logMAR. Reasons for VA testing not being completed will be recorded.

Table 8: Visual acuity in feet and logMAR equivalents for acuity in cycles/cm

Card @ 55 cm (Cycles/cm)	VA equivalent	logMAR
26	20/24	0.06
19	20/32	0.20
13	20/47	0.36
9.8	20/63	0.49

6.5	20/94	0.66
4.8	20/130	0.80
3.2	20/190	0.97
2.4	20/260	1.10
1.6	20/380	1.27
1.3	20/470	1.36
0.86	20/710	1.54
0.64	20/960	1.67
0.43	20/1400	1.84
0.32	20/1900	1.97

HOTV will be attempted on participants who are old enough. HOTV will be performed using the PEDIG ATS-HOTV computerized protocol in each eye separately at a recommended testing distance of 3 meters in all participants. Acuity will be reported in logMAR. Reasons for VA testing not being completed will be recorded.

For primary analysis, the VA endpoint will be the difference between best-corrected VA at baseline and at approximately 1 year (i.e., at the post-cycle 12 assessment).

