9.5. Visual Response

Primary functional outcome is based on visual acuity (VA) and is defined as the difference in VA after approximately 12 cycles of treatment. Eyes above the visual “ceiling” (0.2 logMAR below normal for age or 0.2 logMAR below a previous reliably documented VA) at baseline cannot improve and will be excluded from the analysis of visual response. A significant improvement in VA will be defined as a decrease of ≥ 0.2 logMAR (corrected for age) from baseline (pre-treatment baseline) to end of ~12 cycles of treatment. The analysis will be based on per participant outcome (rather than per eye).

A significant improvement in VA will be defined as a decrease of ≥ 0.2 logMAR from baseline (pre-treatment baseline) to end of ~12 cycles of treatment.

Ophthalmologic (Visual Acuity) Response Criteria

- Visual Responsive ≥ 0.2 logMAR improvement in VA compared to baseline
- Stable VA = does not meet criteria for Improved or Worsening VA compared to baseline
- Visual Progressive Disease ≥ 0.2 logMAR worsening compared to baseline*

* 0.2 logMAR worsening (or up to a 2-card drop in Teller Acuity) will not be considered visual progressive disease at the first on-therapy staging evaluation (at 12 weeks), if the tumor is stable or smaller on MRI. In these cases, a repeat visual acuity assessment will be required 6-12 weeks later to confirm that further visual progression is not occurring. If the repeat visual acuity is stable or improved (0.2 logMAR or less [or a 2 card drop in Teller Acuity or less] from pre-treatment baseline), the patient will remain on protocol therapy. If the visual acuity is now > 0.2 logMAR (or > 2 card drop in Teller acuity) worse from pre-treatment confirmed by a second exam, then the participant will be removed from the protocol.

Visual worsening ≥ 0.2 logMAR in the setting of possible pseudoprogression should be discussed on a case-by-case basis with the study chair. In most cases, patient may continue on study until pseudoprogression vs progression is confirmed. Corticosteroids may be considered, and a short interval repeat eye exam is recommended. If a repeat vision exam shows continued deterioration of visual function, then patient will be permanently removed from therapy and the time of progression will be the date of the initial MRI or vision exam showing progression. See section 10.4 for additional information regarding possible pseudoprogression.

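### Visual response is fixed at the post-cycle-12 exam in sections 9.1 and 9.5, but section 14 lets an earlier exam, or a tumor assessment, stand in for participants who leave early

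*Combined protocol and SAP*

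**What the plan says.** Section 9.1 of the combined protocol and SAP says that "the VA endpoint will be the difference between best-corrected VA at baseline and at approximately 1 year" and identifies that time as the post-cycle-12 exam. Section 9.5 uses the same time point and sets the threshold at 0.2 logMAR, measured "from baseline (pre-treatment baseline) to end of ~12 cycles of treatment". It scores per participant and excludes eyes already above a visual ceiling at baseline. Neither section says what happens when the cycle-12 exam is missing, and neither defines an analysis at cycle 24.

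The visual bullet under Secondary Endpoints in section 14 opens with fixed times: "Evaluation for visual acuity for patients with optic pathways gliomas will be assessed at 12 months and 24 months from starting therapy". Its next sentence changes the rule: "Patient visual outcome will be assessed through the time of the post-12th and 24th cycle visual assessment, or through the last visual assessment time", the latter for those who stopped protocol therapy but remain in follow-up. It ends "or through the last available tumor assessment for patients who are lost to follow-up during this time".

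The endpoint tier also differs. Vision is exploratory in the Protocol Summary and in section 1. It is listed under secondary endpoints in section 14, and section 14.3 counts visual function among the key secondary outcomes.

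**The concern.** A responder rate needs one rule for which exam counts and one rule for who is in the denominator. Here two sections give different answers for the same participant. Someone who goes off study after the cycle-3 exam has no outcome under section 9, yet under section 14 could be a responder at cycle 12, or even cycle 24, on a 12-week reading.

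The lost-to-follow-up clause appears to be carried over from the tumor-response endpoint. Read literally, it supplies no acuity value.

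The analysis sets do not settle the matter. Section 14.3 bases outcome analyses on evaluable participants, and section 14 defines these by one dose and one post-baseline tumor assessment. Section 14.3 also promises parameter-specific sets but defines none for vision. In an open-label single-arm trial, the choice could then be made after the results are known.

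**Working it through.** **The plan's own figure.** No sample size, power or measurement error is given for vision. The only design figure is for tumor response (section 14.2: N = 16, at least 3 responders, 5% against 25%).

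- α = 1 − Σ(x=0 to 2) C(16,x)·0.05^x·0.95^(16−x) = 1 − (0.4401 + 0.3706 + 0.1463) = 0.043
- β = Σ(x=0 to 2) C(16,x)·0.25^x·0.75^(16−x) = 0.197

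Both agree with section 14.2. Vision does not enter this rule.

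**Who is classified differently?**

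| Participant | Sections 9.1 and 9.5 | Section 14, read as last exam |
|---|---|---|
| Has the cycle-12 exam | Change at that exam | Same |
| Off therapy, still followed | Exam near month 12, since eye exams continue | Last exam in the period, normally near month 12 |
| Off study before cycle 12 | No outcome defined | Can be scored on an earlier exam |
| Lost to follow-up before cycle 12 | No outcome defined | Cut at a tumor assessment; no visual value named |

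The second row rests on section 5.4, section 9 and Appendix 4, which require eye exams every 3 months in the first year off therapy. The third row follows from section 3.5: starting new tumor-directed therapy or withdrawing consent ends study participation. Section 14 has no clause that clearly fits these participants.

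**Effect on the rate.** The documents give no expected number of optic-pathway participants and no early-leaver rate, so the counts below are assumptions. Let n be the participants eligible for the visual analysis, k those without a cycle-12 exam, s the responders among the other n − k, and j the leavers whose last exam shows a gain of at least 0.2 logMAR.

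- Section 9, observed exams only: s/(n − k)
- Section 14, last exam: (s + j)/n, with j from 0 to k

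| n | k | s | Section 9, observed | Section 14, last exam |
|---|---|---|---|---|
| 8 | 2 | 3 | 3/6 = 50% | 3/8 = 38% to 5/8 = 63% |
| 10 | 2 | 3 | 3/8 = 38% | 3/10 = 30% to 5/10 = 50% |
| 12 | 2 | 3 | 3/10 = 30% | 3/12 = 25% to 5/12 = 42% |
| 12 | 3 | 3 | 3/9 = 33% | 3/12 = 25% to 6/12 = 50% |

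The upper ends require every early leaver to have gained at the last exam.

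**The tumor clause.** MRI and eye exams share one schedule on therapy, each within 2 weeks either side (section 5.2). At one nominal visit they can be up to 2 + 2 = 4 weeks apart. A cut at the tumor assessment can therefore lose a later eye exam, but usually only within that interval.

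**The case against.** The best defense is that section 14 completes section 9 rather than contradicting it. Section 9 is silent on missing exams, the section 14 bullet begins with fixed times, and the rest could be its missing-data rule. This stands in part. Section 9 does not expressly exclude early leavers, and a reader who infers that it does goes beyond the text. But section 14 never presents the wording as a missing-data rule, and the tumor clause cannot serve as one.

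Two further points stand. Stopping therapy does not stop eye exams, so mainly those who go off study early are affected. The endpoint also has no hypothesis, alpha or sample size.

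A reader might infer something stronger: that section 14 counts a gain at any of the four exams through cycle 12, so that transient or noisy gains become responses. For one eye with no true change and an assumed independent exam error SD of 0.10 logMAR, the false-response chance is 1 − Φ(0.2/(0.10·√2)) = 7.9% at the single cycle-12 exam and, by simulation, 21% at any of four. Over assumed SDs of 0.05 to 0.20 the figures run from 0.2% to 24% and from 0.8% to 51%.

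The documents do not support that reading as the plan's rule. The best-value (nadir) rule in section 14 is written for tumor size only, and the visual bullet itself names 12 and 24 months. A noisy gain at the cycle-12 exam counts under both sections. No measurement SD is given, and section 9.1 requires unreliable tests to be repeated. These rates show why the rule should be stated; they do not estimate error in the plan.

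**Conclusion.** The inconsistency is real and narrow. It affects participants who go off study before the cycle-12 or cycle-24 exam, together with a lost-to-follow-up clause that names the wrong kind of assessment and an endpoint tier that differs between sections.

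The consequence is confined to a descriptive rate. With at most 20 enrolled, and only those with optic-pathway tumors and an eye below the ceiling contributing, two or three reclassified early leavers could move that rate noticeably. In the 10-participant illustration it is 38% under one rule and 30% to 50% under the other. The size rests entirely on assumed counts; the textual conflict does not. It is worth correcting before analysis, but it does not threaten the primary conclusion.

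**What to change.** Rewrite the visual bullet in section 14:

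- Define response as a gain of at least 0.2 logMAR from baseline at the post-cycle-12 exam, and separately at the post-cycle-24 exam. State that it is not the best exam in the window.
- Keep the per-participant scoring and the ceiling exclusion of section 9.5, and define the visual analysis set accordingly.
- Add, as a new rule rather than as something section 9 already says, that participants eligible for the visual analysis with no exam in that visit window count as having no demonstrated response. Report observed-only and last-exam results as sensitivity analyses.
- Remove the tumor-assessment clause from this bullet.
- Give vision one tier throughout the Protocol Summary, section 1 and section 14, including section 14.3.

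This changes wording only; no exam is added. The downside is that the reported visual response rate may be somewhat lower, because a missing exam then counts against response: in the illustration, 3/10 instead of 3/8.
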